Appendix 1 – Contact letter (Danish)

It is not possible to upload foreign language text to ClinicalTrials.gov.

Appendix 2 – Survey in Danish

It is not possible to upload foreign language text to ClinicalTrials.gov.

Appendix 3 – Survey in English

If you experience any issues responding to the survey, please contact [name] by [contact] or email [contact]

Satisfaction

- 1) How satisfied are you with the outcome of your knee replacement surgery?
Very satisfied, Satisfied, Neither satisfied nor dissatisfied, Dissatisfied, Very dissatisfied
- 2) Knowing what your knee replacement surgery did for you, if you could go back in time, would you still have undergone this surgery?
Yes, No, Uncertain

Pain in the operated knee

- 3) [Mandatory] Do you still have pain in the operated knee?
Yes, constantly; Yes, daily; Yes, a few times a week; Yes, more rarely; No
- 4) [Mandatory if 1 ≠ "No"] Please rate your pain in the operated knee by indicating the number that best describes your pain on average during the last week.
0 means 'No pain' and '10' means 'Pain as bad as you can imagine'.

0	1	2	3	4	5	6	7	8	9	10
---	---	---	---	---	---	---	---	---	---	----

What amount of knee pain have you experienced the last week during the following activities?

5) Walking on a flat surface	None	Mild	Moderate	Severe	Extreme
6) Going up or down stairs	None	Mild	Moderate	Severe	Extreme
7) At night while in bed	None	Mild	Moderate	Severe	Extreme
8) Sitting or lying	None	Mild	Moderate	Severe	Extreme
9) Standing upright	None	Mild	Moderate	Severe	Extreme

Activities of daily living

- 10) In total, how much does the pain in the operated knee bother you in your everyday life?
Not at all, A little, Some, Much, Very Much

Does the pain have one or more of the following characteristics?

11) Burning	Yes	No
12) Painful cold	Yes	No
13) Electric shocks	Yes	No

Is the pain associated with one or more of the following symptoms in the same area?

14) Tingling	Yes	No
15) Pins and needles	Yes	No
16) Numbness	Yes	No
17) Itching	Yes	No

Other pain

18) Do you have chronic pain, other than from your operated knee?

Yes; No

[If yes] Please describe your pain condition: _____

Analgesic use

19) Do you take analgesic medication(s) daily or almost daily?

Yes; due to pain in the operated knee; Yes, due to other pain; No

[If yes] Which medication(s)?: _____

Please insert your height and weight

20) [Mandatory] Weight: _____ (kg)

21) [Mandatory] Height: _____ (cm)

Contact

22) Can we contact you again, e.g. regarding your responses?

Yes; No

[if yes] Please insert your contact information (telephone number, email address): _____

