Sample characteristics: Eligible patients are all adult (18 years or older) patients operated with primary total or medial unicompartmental KA for osteoarthritis between August 1 and November 30, 2023. Legally incompetent citizens, i.e., persons with a legal guardian, will not be asked to participate.

For total KA, we will identify patients from the Danish National Patient Register through the Danish Health Data Authority (SKS-code DM17 [knee osteoarthritis] + KNGB20, KNGB30 or KNGB40 [primary total knee arthroplasty]).

For medial unicompartmental KA, we will identify patients from the Danish National Patient Register through the Danish Health Data Authority (SKS-code DM17 [knee osteoarthritis] + KNGB01 or KNGB11 [primary medial unicompartmental knee arthroplasty]).

The sample size calculation is based on the primary outcome in total KA patients. With an estimated 16% incidence of the primary outcome³ and a 70% response rate,¹⁹ 3172 patients are needed to yield a 95% confidence interval of 3 percentage points (14.6-17.6). In our opinion, this level of certainty is appropriate because differences less than this, may be hard to interpret by clinicians and patients. Sampling patients that were operated during 4 months outside holiday season should yield approximately this number of identified patients.⁴

Baseline data of respondents and non-respondents are gathered from the Danish Knee Arthroplasty Register. To evaluate the generalisability of the study, we will report the respondents’ baseline data and compare them to the non-respondents in Table 1.

Survey administration: In an encrypted fashion, the survey will be sent via ‘Digital Post’ which is linked to the unique Civil Registration (CPR) number using the Research Electronic Data Capture (REDCap) software (www.project-redcap.org). A reminder will be sent to non-respondents 14 days after the first letter. Remaining non-respondents are sent a text-message if their telephone number is registered in the electronic patient file.

For questions with an open text field option, two authors (JL, SS) will independently categorise the responses to minimise errors.

Study preparation: We will not advertise the survey and respondents are not rewarded for participation.

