Ethical considerations: The local institutional review board approved the study, and the Danish Health Data Authority will provide contact information for potential respondents. Telephone numbers for non-respondents are found by searching the CPR number in the electronic patient files, but without accessing the patients’ health data. According to Danish legislation, approval from the national ethics committee is neither required nor possible to obtain for survey studies (see attached ‘exempt from notification’ letter from the Danish national ethics committee, S5).

Because we will link survey responses with perioperative data from the Danish Knee Arthroplasty Register, responses are not anonymous. However, only the authors will have access to confidential information and data will be anonymised as soon as possible. Until then, the data are stored pseudonymised at a logged and encrypted drive.

Statistical analyses: The main outcome is the number of patients with moderate or severe persistent postsurgical pain in the operated knee, defined as patients with a numerical rating scale (NRS) score higher than 3.²⁰ We dichotomised the NRS score for our primary outcome because we believe this is more intuitively understood by patients and clinicians. The main outcome will be reported as percentage of all patients with 95% confidence interval, calculated with assumed binomial distribution:

$$p \pm 1.96 \sqrt{\frac{p(1-p)}{n}}$$

Categorical variables, including the individual questions of WOMAC pain domain and DN4 interview, will be reported directly as number of patients (percentage of all patients). The raw NRS score, height and weight are continuous variables and will be reported as median (interquartile range [IQR]) number of respondents.

The five questions in the WOMAC pain domain can be scored 0-4, where 0 is ‘none’ and 4 is ‘extreme’. This results in an overall score of 0-20, which will be reported as median (IQR).

Each of the seven questions in the DN4 interview can be scored 0/1 (no/yes), which results in an overall score of 0-7. A score ≥ 3 constitutes 'possible' neuropathic pain.^{16,17} Both the median (IQR) DN4 interview score and number of patients (percentage of all patients) with possible neuropathic pain will be reported.

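### The printed questionnaire does not identify which knee is meant, so patients with both knees replaced may rate the other or the worse knee, which can bias the primary outcome

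*Combined protocol and SAP*

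**What the plan says.** Under Methods, Sample characteristics, the plan states: "Eligible patients are all adult (18 years or older) patients operated with primary total or medial unicompartmental KA for osteoarthritis", with the operation "between August 1 and November 30, 2023". The only stated exclusion is having a legal guardian. The procedure codes are listed without side. Nothing is said about replacement of the other knee before, during or after the window, or about which knee counts if both were operated within it.

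The main outcome (Statistical analyses) is moderate or severe pain in the operated knee, "defined as patients with a numerical rating scale (NRS) score higher than 3", reported as a percentage of all patients.

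In Appendix 3 the knee or operation is identified as follows:
- Question 1: "How satisfied are you with the outcome of your knee replacement surgery"
- Question 3, which decides whether questions 4-17 are shown: "Do you still have pain in the operated knee"
- Question 4, the primary outcome: "Please rate your pain in the operated knee by indicating the number that best describes your pain on average during the last week"
- Questions 5-9, the WOMAC pain items: "What amount of knee pain have you experienced the last week during the following activities"
- Question 18: "Do you have chronic pain, other than from your operated knee"

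The DN4 items (11-17) refer only to the pain. The printed header holds contact details only. The Danish contact letter and Danish questionnaire (Appendices 1 and 2) are not in the public file.

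**The concern.** The wording presumes one operated knee per patient. For a patient with two replaced knees the phrase has no single meaning, and that patient is eligible. The ambiguity enters twice on the primary outcome: at question 3, where a painful other knee can turn a No into a Yes, and at question 4, where the score itself may belong to the other or the worse knee. Questions 18 and 19 depend on the same distinction, so they cannot resolve it.

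The planned confidence interval reflects sampling error only. A shift from rating the wrong joint would not show in it, and more respondents would not reduce it. Individual misclassification also matters where the plan reuses the answers patient by patient, as in the follow-on validation of prescription registries for identifying persistent pain (Knowledge dissemination).

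**Working it through.** **Inputs from the plan (Sample characteristics).** Incidence 16%, response rate 70%, 3172 patients, intended 95% confidence interval 3 points wide (14.6-17.6).

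**Inputs assumed, because the documents do not give them.** *b*, the share of respondents with both knees replaced; *w*, the share of those who rate the worse knee; *rho*, the within-patient correlation of NRS > 3 between the two knees. The 16% is taken as the risk for each replaced knee.

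**1. The plan's precision.** Respondents: 3172 × 0.70 = 2220. Half-width: 1.96 × √(0.16 × 0.84 / 2220) = about 1.5 points, an interval of 14.5-17.5 with total width 3.05. For a width of exactly 3 points the plan's formula needs 1.96² × 0.16 × 0.84 / 0.015² = 2295 respondents, and 2295 / 0.70 = 3279 patients. The stated 3172 is therefore not reproduced exactly, but the gap has no bearing on this point. The benchmark is a half-width of about 1.5 points.

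**2. Observed rate if a patient rates the worse of two knees.**
q = 2p − [p² + rho × p(1 − p)], with p = 0.16.
- rho = 0: q = 0.32 − 0.0256 = 0.294
- rho = 0.3: q = 0.32 − (0.0256 + 0.0403) = 0.254

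**3. Shift in the overall percentage.** Shift = b × w × (q − 0.16), where q − 0.16 is 9.4 points (rho 0.3) to 13.4 points (rho 0).

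| Bilateral share b | Half rate the worse knee (w = 0.5) | All do (w = 1) |
|---|---|---|
| 10% | +0.5 to +0.7 | +0.9 to +1.3 |
| 20% | +0.9 to +1.3 | +1.9 to +2.7 |
| 30% | +1.4 to +2.0 | +2.8 to +4.0 |

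**4. Where the shift equals a half-width of 1.5 points.** b × w = 1.5 / 13.4 = about 11% of all respondents under independence, or 1.5 / 9.4 = about 16% at rho 0.3.

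**5. If patients rate the wrong knee rather than the worse one.** With equal risk in that knee (16%), the net shift is zero, although individuals are misclassified. If that knee's risk were 10%, then b = 30% and w = 50% would give 0.15 × (10 − 16) = −0.9 points.

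**The case against.** The strongest objection is that the public file is incomplete. Patients receive the Danish letter and the Danish form, and neither can be seen here. A letter naming the operation would tell the patient which knee is meant, even though the answers are entered elsewhere. This stands, and it makes the point conditional. The plan's text describes the letter only as carrying contact information, so the documents do not settle the matter.

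Three stronger readings are tempting and should not be drawn:
- *The primary outcome is biased.* The documents do not show that patients rate the worse knee, and step 5 shows that rating the wrong knee can leave the percentage unchanged or lower it.
- *The analysis cannot deal with it.* Patients are identified through a national register by procedure code, and answers are linked to the arthroplasty register. Two operations in the window may already show in the extract, and earlier ones might be sought. No such step is planned, however, and a flag would not reveal which knee was rated.
- *The comparison of respondents with non-respondents is damaged.* Table 1 uses baseline and surgical data only, so a mis-rated knee leaves it unchanged.

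The WOMAC stem taken alone is weak evidence, since it sits under a section heading about the operated knee. Rewording items would also have a price: WOMAC and DN4 are used as validated instruments, several questions were matched to the 2004 survey, and a patient panel tested the form. That argues for an instruction line rather than for changing the items.

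**Conclusion.** The point holds in conditional form. The questionnaire as printed does not identify the index knee, patients with two replaced knees are eligible, and no index-knee rule is given. Unless the Danish material names the operation, this can bias the primary outcome. Worse-knee rating pushes it up; wrong-knee rating has a net effect that may be zero or of either sign.

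Neither the bilateral share nor the answering behaviour is in the documents, so the size is not established. Under the stated assumptions the upward shift runs from well below the planned half-width to above it. With half of bilateral patients rating the worse knee, it reaches 1.5 points only near a 30% bilateral share, and there only at low correlation. This is a cheap improvement to the primary measurement, best made before the survey is sent, not a demonstrated error in the result.

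**What to change.** 1. Show the date of the index operation, and its side if the register extract holds it, in the REDCap header or in an instruction line above question 1 and again above the section on pain in the operated knee. Leave the wording of the WOMAC, DN4 and 2004-survey items unchanged. If the Danish letter or form already names the operation, say so in the protocol.
2. State in advance which knee is the index knee for patients with two operations in the window.
3. Add one optional item, such as *Has your other knee also been replaced?*, placed outside questions 4-17 so that patients without pain also see it. Alternatively, flag contralateral replacement from the register.
4. Add one sentence to Statistical analyses: the primary outcome is repeated without patients whose other knee has been replaced. This is a check rather than a correction, because those patients may differ in other ways. It also costs some precision: at an assumed 20% bilateral share, 2220 × 0.80 = 1776 respondents remain and the half-width becomes 1.96 × √(0.16 × 0.84 / 1776) = about 1.7 points.

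The cost is one more optional question, a small departure from the panel-tested form, and one or two fields filled in automatically. The sample size and the interval formula do not change. If the survey has already been sent, the register flag and the sensitivity analysis are still possible.

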We are not aware of previous assessments of long-term pain outcomes in unselected Danish patients operated with KA. The most widely used numbers originates from a systematic review published in 2012 that used data collected in various countries between 1995-2006.² An updated investigation is important for several reasons. First, surgical techniques and equipment have evolved over the years. Second, introduction of standard treatment with high-dose glucocorticoids should, in theory, have reduced central sensitisation, which is a key aspect of persistent postsurgical pain.^{7,8} Third, implementation of early mobilisation and other enhanced recovery after surgery (ERAS) elements have reduced the mean length of hospital stay from around 10 days in 2000 to a single day in 2021.⁴

For these reasons, we aim to investigate the satisfaction and incidence of persistent pain after KA for osteoarthritis.

Methods

The study is registered at the capital region of Denmark's regional research listing (Pactius) with identifier P-2023-4, approved 4 January 2023. This protocol is registered at ClinicalTrials.gov and is **currently under review**. The resulting paper will be reported according to the CROSS checklist for standardised reporting of survey studies.⁹ Wherever needed, a trained linguist translated questions from English to Danish and vice versa. The Danish and an English version of the questionnaire will be available in the final publication.

Study design: This study is a nationwide cross-sectional survey.

Patient involvement: A panel of KA patients helped develop the questionnaire, i.e., testing and selecting the questions.

Questionnaire: The questionnaire is composed of 22 questions, however patients answering "No" to question 3 skips questions 4-17 concerning pain in the operated knee. Only questions 3, 4, 20, and 21 are mandatory because we wanted to avoid non-respondents. The contact letter in Danish (S1) and full questionnaire in Danish (S2) and English (S3) can be found in the supplementary material. Contact information for the first author (JL) is supplied in the contact letter and the header of the questionnaire, in case the patients have difficulties with filling in the questionnaire, believe they have been contacted mistakenly etc. We used similar or identical questions to those in a survey conducted in 2004 to increase our ability to compare results (i.e., questions 3-5, 8, 10 and 18).¹⁰

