The 1st question assesses overall satisfaction with surgery and have been translated directly from the questionnaire used by the Swedish Arthroplasty Register to enable direct comparison.³

Question 2 assesses willingness to repeat surgery, as described by Chestworth et al..¹¹

Question 3 assesses pain frequency with the same response options as the 2004 survey.¹⁰ This question is mandatory due to branching purposes, i.e. respondents without pain can skip questions 4-17.

Question 4 is the 11-point numerical rating scale (NRS) for knee pain, which is widely used and recommended.^{12,13} To facilitate comparison with other studies, we assessed average pain in the last week.¹² This question is also mandatory because it is our primary outcome.

Question 5-9 is the pain dimension of the likert-scale version 3.1 Western Ontario and McMaster Universities Osteoarthritis Index (WOMAC).¹⁴ The instrument is validated for osteoarthritis patients and specifically recommended by the International Association for the Study of Pain (IMMPACT).¹³

Question 10 assesses pain interference on everyday activities. Pain interference is often included in core outcome sets for clinical trials^{13,15} and it is recommended to use disease-specific interference.¹³

Question 11-17 are the Douleur Neuropathique 4 questions (DN4) interview, which can be used to estimate the number of patients with ‘possible’ neuropathic pain.^{16,17} We chose to the DN4 interview over other neuropathic pain measures because it is widely used and validated, short, and available in Danish (from www.mapi-trust.org).¹⁶

Question 18 assesses other chronic pain conditions with an open text field, which we will later categorise. We believe this is more accurate than allowing patients to categorise their pain condition from a predefined list of options.

Question 19 assesses patient-reported use of analgesics, including if the analgesics are taken for pain in the operated knee or not. Again, the type of analgesics is typed into an open text field, as to not restrict respondents to specific medications and to enable responses with typos.

Questions 20 and 21 are on the patient’s current height and weight, recently found to be valid in a Danish E-survey setting.¹⁸

Finally, in question 22 we ask for permission to contact respondents again later.

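### The printed English stem of the WOMAC pain items (questions 5-9) does not name the operated knee, so some respondents may count pain in the other knee

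*Combined protocol and SAP*

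**What the plan says.** The Methods (Questionnaire paragraph) state that a respondent who answers No to question 3 "skips questions 4-17 concerning pain in the operated knee". Questions 5-9 fall in that range. The Methods identify them as the WOMAC 3.1 Likert pain dimension.

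In Appendix 3 (Survey in English), question 3 asks "Do you still have pain in the operated knee", question 4 begins "Please rate your pain in the operated knee by indicating the number that best describes your pain on average during the last week", and question 10 asks "In total, how much does the pain in the operated knee bother you in your everyday life". The shared stem of questions 5-9 is "What amount of knee pain have you experienced the last week during the following activities".

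Under Statistical analyses, the five items are each reported as numbers and percentages. They are also summed to a 0-20 score, reported as a median with interquartile range. No test, threshold or sample size is attached to that score.

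**The concern.** The construct in the Methods is pain in the operated knee, but the printed words of the five items ask about knee pain in general. Eligibility requires a primary knee arthroplasty for osteoarthritis and does not exclude a painful other knee. A respondent who takes the stem at face value may therefore include a joint that was not operated on.

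The WOMAC score and its five item percentages are the survey's activity-specific pain results. If some respondents count the other knee, these results no longer describe quite the same thing as the NRS and interference items beside them. Individual scores cannot be corrected afterwards.

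**Working it through.** No figure in the plan depends on this wording, so there is nothing to reproduce. The check is a comparison of texts, followed by an illustration on assumed values.

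**Step 1. The items side by side (Appendix 3).**

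| Item | Block heading above it | Names the operated knee? | Time frame |
|---|---|---|---|
| Question 3 (filter) | Pain in the operated knee | Yes | Present, by frequency |
| Question 4 (primary outcome) | same block | Yes | Last week |
| Questions 5-9 (WOMAC pain) | same block | No | Last week |
| Question 10 (interference) | Activities of daily living | Yes | Everyday life, no period given |

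Question 10 opens a new block, so it had reason to name the knee again. Question 4 stands under the same heading as questions 5-9 and still names it. The form therefore did not rely on the heading alone one line earlier.

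**Step 2. What the context does.** Three cues point to the operated knee: the heading, question 4 directly above with the same one-week recall, and the filter at question 3. The filter means that only people who report pain in the operated knee see the items. It limits who answers, but not which knee they rate.

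**Step 3. Where the gap remains.** Question 3 accepts the answer that pain occurs more rarely than a few times a week. Such a respondent proceeds to questions 5-9, which ask about the last week. The operated knee may not have hurt in that week. If the other knee did, reporting pain on stairs or in bed is a truthful answer to the printed stem.

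**Step 4. Whether the plan would notice.** Other-knee pain can surface only in question 18, a Yes/No item with a free-text follow-up. Two authors will categorise the text independently. The question is not mandatory (only 3, 4, 20 and 21 are), and the Statistical analyses section plans no use of it to qualify the WOMAC score.

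**Step 5. Size, on assumed values only.** Let q be the share of those answering questions 5-9 who count the other knee, and k the number of the five items that this raises by one grade. The shift in the mean 0-20 score is q × k × 1.

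- q = 0.10, k = 1: 0.10 × 1 = 0.1 points
- q = 0.20, k = 3: 0.20 × 3 = 0.6 points
- q = 0.50, k = 5: 0.50 × 5 = 2.5 points

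Both q and k are assumptions; the documents supply neither. The sign is also an assumption. It is positive if respondents add the other knee's pain. It is negative for anyone who rates only a less painful other knee or averages the two. The plan reports the median, and its shift depends on a score distribution that the documents do not give.

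**The case against.** The strongest reply is that nobody reading the form in order would be in doubt. The heading, question 4 and the filter all concern the operated knee, and pain elsewhere has its own later block. Questions 11-17 also speak only of the pain, without repeating which knee. A patient panel tested the questions. Patients receive the Danish form, which is not reproduced, so the omission may exist only in the English rendering. Questions 5 and 8 are among those kept similar or identical to a 2004 survey, so rewording could weaken that comparison.

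Most of this stands. The intended reading is the likelier one, and the Danish text may already be specific. It does not remove the mismatch in Step 3, and panel testing does not show that this ambiguity was looked for. The cited 2004 survey was of hip arthroplasty, so joint-specific wording probably had to be adapted in any case.

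Two stronger readings are tempting, and the documents support neither. A reader might infer that the stem makes patients rate their worse knee; nothing in it asks for the worse knee or for both. A reader might also infer that the score is biased upwards by a stated amount, or that the median shifts by a grade. Any such figure needs a rate of other-knee pain, a rate of misreading, a severity for the other knee and a score distribution, all of which would have to be invented.

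**Conclusion.** The point holds as a minor ambiguity in wording. The printed English stem of questions 5-9 is less specific than the construct in the Methods, and the surrounding cues make the intended reading likely without securing it. The group most exposed is respondents with infrequent pain in the operated knee and a painful other knee.

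The size of any bias cannot be derived. The range of 0.1 to 2.5 points above only shows how the arithmetic behaves under assumed inputs and is not an estimate. An increase is the natural expectation if respondents add the other knee's pain, but a decrease is possible for some, so the direction is not established either. The primary outcome (NRS above 3, from question 4) is unaffected. All of this assumes that the Danish stem matches the English one, which cannot be checked from the documents.

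**What to change.** - **Check the Danish stem.** If it already names the operated knee, correct only the English version.
- **If it does not, and the survey has not been sent:** in both versions, replace the words 'knee pain' in the stem with 'pain in your operated knee', and leave the rest of the sentence unchanged.
- **If the survey has been sent:** state the ambiguity as a limitation. Show the WOMAC pain score separately for respondents with and without other knee pain, as categorised from question 18. This is a partial check only. Question 18 is optional and asks about chronic pain, and the two groups may also differ in true pain in the operated knee, so the difference between them does not measure the bias.

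The cost is one phrase in the REDCap form and the two survey appendices, or one sentence and an extra table row if already fielded. The drawback is a slight departure from the instrument's stem and possibly from the wording kept for comparison with the 2004 survey (questions 5 and 8). The paper should note the change.

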We do expect some missing data because incomplete questionnaires may be submitted. Generally, responses will not be imputed. However, we will impute values to calculate summary scores of the WOMAC pain domain and DN4 interview as the median of the reported values within the instrument.

We do not plan to adjust for non-representativeness, but as previously mentioned, baseline characteristics (age, sex, and ASA score) and surgical details (type of anaesthesia, operation length, use of local infiltration analgesia (LIA), use of cement, and surgical complications) of respondents and non-respondents are presented in Table 1.

Data is handled in the most recent version of R (www.r-project.org).²¹

Knowledge dissemination

The survey will be fully reported in an international peer-reviewed journal. In addition, the responses from this survey will be pooled with responses from a similar survey on hip pain. The combined data will be used in two additional studies: 1) to validate the use of prescription registries on analgesic for identifying patients with persistent postsurgical pain,²² and 2) to investigate associations between weight and weight-change and the different outcomes. Both will be published in peer-reviewed journals.

We seek to make the papers freely available (e.g., as preprint at www.medrxiv.org or through open-access publication) and to store the full dataset at the Danish national archive (www.rigsarkivet.dk). Moreover, the results will be presented at meetings and conferences, predominantly for orthopaedic surgeons, anaesthetists, pain specialists, and other health-care personnel working with this patient group.

The systematic review from 2012 that we seek to build on is widely used, even though the data may be outdated.² This study is necessary to avoid false assumptions regarding the contemporary risk of persistent pain after KA. We are certain that the results from this study will be used by clinicians to guide patients in their decision to undergo KA or not.

References

1. Gademan, M. G. J., Hofstede, S. N., Vliet Vlieland, T. P. M., Nelissen, R. G. H. H. & Marang-van de Mheen, P. J. Indication criteria for total hip or knee arthroplasty in osteoarthritis: a state-of-the-science overview. *BMC Musculoskelet. Disord.* **17**, 463 (2016).

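### As printed, question 19 cannot record patients who take analgesics for both the operated knee and other pain, and one shared medication field cannot link a named drug to a reason

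*Combined protocol and SAP*

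**What the plan says.** The Methods (Questionnaire, description of question 19) say that the item assesses patient-reported analgesic use, "including if the analgesics are taken for pain in the operated knee or not". The type of drug is collected as open text.

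Appendix 3 – Survey in English prints the stem as "19) Do you take analgesic medication(s) daily or almost daily" and the answers as "Yes; due to pain in the operated knee; Yes, due to other pain; No". A single open field for the medication names follows any yes. No answer covers both reasons, and nothing tells the respondent to tick all that apply.

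The question just before it reads "18) Do you have chronic pain, other than from your operated knee", so pain elsewhere is expected. Where several answers may apply, in questions 11–17, the survey signals it: the first stem reads "Does the pain have one or more of the following characteristics", and each item has its own yes/no.

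Under Survey administration, two authors "will independently categorise the responses to minimise errors" for open-text questions. No rule is given for assigning a drug to a pain source. Under Statistical analyses, categorical variables are reported as number and percentage of all patients. Under Knowledge dissemination, the responses, pooled with those of a hip survey, will serve a further study "to validate the use of prescription registries on analgesic for identifying patients with persistent postsurgical pain".

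**The concern.** The item is meant to separate knee-related analgesic use from other use, but its printed answers do not cover everyone. A patient who takes analgesics daily for the operated knee and also for, say, back pain has two true reasons and, on the printed layout, one answer to give. Different patients will resolve this differently, and the data will not show how.

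Two results are exposed. The first is the percentage using analgesics for the operated knee. Any error there is not random, because it arises only in people with another pain. The second is the drug list: when both reasons apply, drugs for the knee and drugs for the other pain end up in the same field. This matters when asking why a registry-based rule flags a patient, since a prescription for another pain is an obvious source of false positives.

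Question 19 is also not among the mandatory items (3, 4, 20 and 21). A respondent who finds no fitting answer can skip it, and responses are generally not imputed.

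**Working it through.** The plan states no figure for analgesic use, so there is nothing to reproduce. The check has two parts.

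**1. What the item can record**

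| Patient's true situation | If one answer is allowed | If two ticks are allowed |
|---|---|---|
| Knee only | Correct | Correct |
| Other pain only | Correct | Correct |
| Both reasons | Recorded as one reason; drugs not attributable | Both reasons recorded; several drugs still not attributable |

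The problem is therefore confined to daily or almost daily users with both reasons. The shared medication field fails for them under either form type. Independent categorisation by two authors reduces coding errors but cannot recover a link that was never collected.

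**2. Possible size (illustration; all three inputs are assumptions)**

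- T = true share using analgesics for the operated knee: 15%
- d = share of those who also use them for other pain: 20–60%
- s = share of these dual-reason users who tick the other-pain answer: 0–50%

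Observed knee use = T × (1 − d × s). Understatement = T × d × s.

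| d | s = 0 | s = 25% | s = 50% |
|---|---|---|---|
| 20% | 15.0% | 15 × (1 − 0.05) = 14.25% | 15 × (1 − 0.10) = 13.5% |
| 60% | 15.0% | 15 × (1 − 0.15) = 12.75% | 15 × (1 − 0.30) = 10.5% |

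The understatement runs from 0 to 15 × 0.60 × 0.50 = 4.5 points. The 50% limit on s is itself an assumption. If every dual-reason user ticked other pain, the d = 60% row would give 15 × 0.60 = 9 points.

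For scale, Sample characteristics gives 3172 patients and a 70% response rate, so 3172 × 0.70 ≈ 2220 respondents. At 15%, the 95% half-width by the plan's formula is 1.96 × √(0.15 × 0.85 / 2220) ≈ 1.5 points. The possible bias thus ranges from nothing to about three times the sampling error. If some respondents skip question 19, the half-width is somewhat larger.

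At s = 0 the knee percentage is correct, but other-pain use is understated and drugs taken for the other pain are listed under the knee.

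**The case against.** Much of the case against limits the point, and several stronger readings fail.

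- **Form type.** A reader might infer that patients are forced to choose one answer. The documents do not state the REDCap field type, the Danish form was not uploaded, and a text listing looks the same for radio buttons and checkboxes. The layout suggests single choice, because it matches question 3 and differs from questions 11–17, but that is not proof. This answers the first half of the point if the form is multi-select. It does not answer the shared medication field.
- **Direction.** A reader might infer that knee use must be understated. The knee answer comes first, the survey is about the knee, and that answer is literally true for a dual-reason user. If all of them choose it, the knee percentage is right. Zero bias therefore belongs in the range.
- **Who is affected.** A reader might extend the problem to everyone with more than one pain source. It reaches only those who take analgesics daily or almost daily for both.
- **Registry validation.** A reader might infer that question 19 is the reference standard for that study. The documents do not say so. The target condition there is persistent postsurgical pain, and Statistical analyses defines moderate or severe persistent pain in this survey by NRS above 3. The validation's own analysis is not specified here. Question 19 can help interpret it, and no more can be claimed.
- **Safeguards.** A patient panel tested the questions. Questions 3 and 18 identify respondents with both knee pain and other chronic pain, and question 22 asks permission to get back in touch about responses. These allow bounds and some clarification, but they do not supply the missing link between drug and reason.

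**Conclusion.** The point stands as a minor, inexpensive improvement to a secondary item. As printed, question 19 has no answer for dual-reason users, so their knee-related use may be misclassified. The single medication field cannot tie a named drug to a reason for them, whatever the field type.

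The primary outcome does not use this item and is untouched. The effect is on the descriptive analgesic result and on how analgesic data are interpreted in the registry validation. The size cannot be derived from the documents. Under the assumed inputs (15% knee use, 20–60% of these with both reasons, 0–50% of those ticking other pain) the understatement is 0 to 4.5 points, and zero is a realistic end of that range.

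**What to change.** - Add an answer such as 'Yes, due to both', or make the item explicitly multi-select. Count it as operated-knee use.
- Show one medication field per ticked reason: one for the operated knee, one for other pain. A drug taken for both can be entered in both.

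The cost is one response option and one branched text field in REDCap, with slightly more free text for respondents to complete and for the two authors to categorise. No extra patients are needed.

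If the survey has already been sent:

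- State how question 19 was set up and coded, and report dual-reason use as a limitation.
- Give bounds for knee-related use. The lower figure counts those who ticked the knee answer. The upper figure adds those who ticked other pain but report knee pain at question 3 and chronic pain elsewhere at question 18. Because question 18 covers chronic pain only, a looser upper figure drops that condition.
- Where question 22 permits contact, clarify the reason with respondents in this ambiguous group.
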